7.3 LOST TO FOLLOW-UP

A participant will be considered lost to follow-up if he or she fails to return for 2 scheduled visits and is unable to be contacted by the study site staff.

The following actions must be taken if a participant fails to return to the clinic for a required study visit:

- The site will attempt to contact the participant and reschedule the missed visit within 10 days and counsel the participant on the importance of maintaining the assigned visit schedule and ascertain if the participant wishes to and/or should continue in the study.
- Before a participant is deemed lost to follow-up, the investigator or designee will make every effort to regain contact with the participant (where possible, 3 telephone calls, 3 e-mail messages and, if necessary, a certified letter to the participant's last known mailing address or local equivalent methods). These contact attempts should be documented in the participant's medical record or study file.
- Should the participant continue to be unreachable, he or she will be considered to have withdrawn from the study with a primary reason of lost to follow-up.

8 STUDY ASSESSMENTS AND PROCEDURES

8.1 EFFICACY ASSESSMENTS

Primary efficacy outcome

The Unified Multiple System Atrophy Rating Scale (UMSARS) total score. The primary outcome measure will be the total UMSARS score progression at week 48 compared to baseline. UMSARS is a validated, disease-specific scale representing the diverse signs and symptoms in MSA (36). It can assess rates of progression and is sensitive to change over time (37). It has an Activities of Daily Living score (UMSARS-1, 12 questions) that evaluates motor including autonomic activities and the Motor Examination score (UMSARS-2, 14 questions). UMSARS-3 measures supine/standing BP and UMSARS-4 is a disability scale (1-5). Higher scores on the UMSARS scales mean poorer health. The UMSARS will be determined by the same investigator at each study visit to ensure consistency. This investigator has undergone specific UMSARS training and has extensive experience in performing this scale. The investigator rating the UMSARS will be blinded to the previous UMSARS score of the patient as well as to the treatment group assignment of the subject.

Secondary efficacy outcomes

The Unified Multiple System Atrophy Rating Scale (UMSARS) part 1 and part 2. Secondary outcome measures include the UMSARS-2 score (neurological examination) progression at week 48 compared to baseline; the UMSARS-1 score (activity of daily living) progression at week 48 compared to baseline.

Neuroimaging: We will compare several diffusion parameters of the individual and combined putamen in subjects using brain magnetic resonance imaging (MRI) obtained at baseline and after 48 weeks. Diffusion-based MRI techniques measure how the random movement of water is altered in normal and disease nervous tissue. Diffusion MRI data can be analyzed with a mathematical tensor that provides

model parameters for the mean diffusion of water (the apparent diffusion coefficient, or “ADC”), the degree of diffusion orientation dependence (fractional anisotropy, or “FA”) and the dominant orientation of water diffusion in an individual image voxel (first Eigen vector). In most neurodegenerative conditions, the tissue environment sampled by water becomes less organized over time and this is reflected by increasing ADC and decreasing FA. Compared to PD, increased putaminal ADC in MSA-P has been consistently reported, even in early disease stages (42, 55-59). Putaminal ADC changes have been reported to be a highly sensitive MRI marker of disease progression in patients with MSA and has been used previously as neuroimaging outcome measure in previous clinical trials of MSA (41, 42).

MRI will be carried out with a state-of-the-art 1.5-T MRI system and 24-channel head coil (Aera, Siemens Healthcare, Erlangen, Germany) – note, while 3-T has some signal-to-noise advantages, many MSA patients have cardiac pacer wires that make 3-T imaging difficult or impossible to obtain routinely. First a volumetric 3D T1-weighted MR-RAGE (TR/TE/TI 10/2/600 ms) and volumetric 3D SPACE FLAIR MRI sequences will both be obtained with 1-mm isotropic resolution (10 minutes total). Routine 3D susceptibility-weighted imaging will be obtained (5 min). Finally axial high-angular resolution diffusion MRI will be obtained of the whole brain using 3-mm isotropic resolution using echoplanar imaging, parallel imaging and 2-slice acceleration with simultaneous multi-slice acquisitions (TR/TE = 7000/100 ms, b = 0 and 1500 s/mm², 30 gradient directions). These data will be analyzed with inline scanner diffusion tensor model and parameter maps of ADC, FA and fiber orientation generated. These will be co-registered with the volumetric data and manual regions-of-interest drawn to include the entire left and right putamen to extract mean ADC and FA. A secondary neuroimaging aim in this study will be to determine whole brain, cortical, white matter and individual structure volumes at baseline and after 48 weeks using automated FreeSurfer analysis as described in the literature (67).

[name], Assistant Professor of Radiology at the NYU Center for Advanced Imaging Innovation and Research and Director of the NYU Brain Mapping Service (which performs fMRI and diffusion tractography for neurosurgical planning) will supervise creation of the MRI protocol, data acquisition, diffusion analysis and interpretation of the neuroimaging data. [name] is an academic neuroradiologist with MD/Ph.D. training in diffusion MRI and 6 years of experience performing advanced diffusion acquisitions in patients with MSA, Parkinson disease and other neurodegenerative diseases, brain tumors and epilepsy.

Retinal optical coherence tomography: Retinal nerve fiber layer thickness progression at week 48 compared to baseline. The use of optical coherence tomography (OCT) is emerging as a non-invasive fast technique to measure the thickness of the retinal layers. Even though patients with MSA only rarely have visual complaints, recent studies by our group using OCT showed that the retina of patients with MSA have consistent atrophy of the peripapillary retinal nerve fiber layer (RNFL) and to a lesser extent the macular ganglion cell layer (GCL) complex (13). These abnormalities are progressive overtime and have been recently confirmed by pathological examination in the retinas from three patients with MSA (12, 14). In brief, high definition OCT will be performed in a darkened room by the same trained personnel using standardized Food and Drug Administration (FDA)-approved equipment to evaluate the structure of the eye (Cirrus 4000, Carl Zeiss, CA, USA). Images will be acquired in the seated position with the subjects facing the OCT equipment. Subjects were instructed to fixate their gaze at a green target during the scan. Each subject had both eyes scanned at least three times using two standard acquisition protocols: macular cube (512x128 line scans) and optic disc cube (200x200 line scans). In both protocols the scanned area was a 6-mm cube with no signal averaging. The quality of the obtained images was assessed by evaluation of the signal strength (a value from 0-10 in arbitrary units)

automatically provided by the system. Only scans with signal strength above 6 units were included in the analysis. In some patients with MSA, involuntary eye movements will make the test difficult to obtain. In such cases, repeated scans will be performed to obtain at least three scans without eye movement artifacts. The scan with the best resolution will be used for analysis. For OCT quantification, two automatic segmentation algorithms will be used to determine the RNFL and ganglion cell complex (GCC) thicknesses (Cirrus 4000, Carl Zeiss, CA, USA). For the RNFL analysis, an optic disc cube of data (200x200-line scans) centered in the optic nerve head will be acquired. Subsequently, a recognition algorithm detected the inner (vitreoretinal interface) and outer (inner plexiform layer) border of the RNFL, from a 1.73-mm diameter circle will extract from the optic nerve cube and centered in the optic nerve head. The distance between the two lines will be measured as RNFL thickness at specific quadrants around the optic nerve: temporal, superior, nasal, inferior and global. For the GCC analysis the macular cube 512x128 centered in the foveal pit will be used. A different recognition algorithm will be applied to detect the outer border of the RNFL and the inner plexiform layer. The GCC analysis will evaluate the thickness of the ganglion cell plus inner plexiform layers. The average, minimum and sectorial thicknesses of the GCC will be measured in an elliptical annulus (vertical inner and outer radius of 0.5 mm and 2.0 mm respectively; horizontal inner and outer radius of 0.6 and 2.4 mm, respectively) around the fovea. The GCC thickness will be measured in different locations in the macula, around the foveal center: temporal-superior, superior, nasal-superior, nasal inferior, inferior, temporal-inferior, and global. The global RNFL and GCC thickness values, as well as those at each specific quadrant, expressed in micrometers (μm), will be used for analysis, although only the total RNFL will be used as secondary outcome measure.

Exploratory outcomes

Measurement of αSyn in CNS-derived extracellular vesicles (Evs): As exploratory outcome measure we will measure the concentration of αSyn in neuronal and oligodendroglial Evs isolated from patients' serum at baseline, on week 24, and on week 48. Recently, exosomes have been implicated in the dissemination of misfolded proteins in a variety of neurodegenerative disorders, including Parkinson disease.(68) Exosomes are Evs of 30–200 nm diameters that are released from various cells including neurons.(69) Exosomal release and transport of αSyn followed by intracellular uptake and induction of toxicity and cell death has been reported by several groups *in vivo* and *in vitro*.(70, 71) Several groups also have measured exosomal αSyn particles in cerebrospinal fluid (CSF) of patients with synucleinopathies.(72) However, because the lumbar puncture required for obtaining CSF is rather invasive and patients often refuse it, we opt to use a new methodology in which brain-derived Evs will be isolated from serum. The methodology has been introduced originally in 2014 in studies of Alzheimer's disease and frontotemporal dementia(73-75) and in two recent studies was applied also to patients with Parkinson disease.(76, 77) This methodology has been improved by [name] team at UCLA, who has been able to distinguish among healthy controls, patients with Parkinson disease, and patients with MSA with high sensitivity and specificity (*see preliminary data section*). Our group has been collaborating with [name] and contributed part of the samples included in the preliminary data. Using the same protocol, we will obtain samples from the patients included in the study proposed here and ship them to the [name] laboratory for analysis. In brief, 10 ml of blood will be extracted from each patient and centrifuged immediately to extract the serum. Because αSyn is one of the major biomarkers in our analysis, and in addition to neurons it exists in high levels in erythrocytes, it is crucial to separate the serum within a 20-minute window from drawing the blood, before hemolysis begins. The serum samples will be flash frozen immediately and stored at -80C. They will then be shipped on dry ice to [name] laboratory at UCLA, where the quantification of exosomal αSyn particles

will be performed by operators blinded to the study intervention. [name] will receive only de-identified samples. He will have no way to link the samples to the subject's identities or PHI.

8.2 SAFETY AND OTHER ASSESSMENTS

The primary safety outcome is number of participants (%) who discontinue the study due to AE.

Secondary safety outcomes include active monitoring for severe adverse events (SAE's) throughout the trial. Specific SAE's are anticipated to be related to sirolimus. These selected SAE's include mucositis, anemia, thrombocytopenia, hyperglycemia, hyperlipidemia, proteinuria, renal failure, pneumonitis, and infection. The occurrences of these safety outcomes by treatment arm will be reported in bi-annual safety reports to the IMM. We will also report counts and proportions of mortality for each treatment arm (by rhythm), along with the number of SAEs that are probably or definitely related to mortality.

Adverse events will be recorded from the time a participant has signed the Informed Consent Form and throughout the 12 months of the study, even if they prematurely discontinue the study drug. They should be reviewed and updated at each subsequent visit and during any phone contact with the participant. Participants will be instructed to call a provided number if they experience AE between scheduled visits. An unscheduled visit may be needed so that the participant can be assessed.

Safety laboratory evaluations. Safety laboratory evaluations will be performed at screening, baseline, during each study visit and at termination visit. In addition, laboratory evaluations at months 2, 4, 5, 7, 8, 10 and 11 will be performed either at the NYU Dysautonomia Center or locally if the patient is unable to come to NYU. HIV testing, hepatitis B and C, QuantiFeron and serum pregnancy testing (women) will be performed only at screening. In addition, the following tests will be performed during all monthly safety assessments (Visit 7 and onwards).

- *Complete blood count with differential – approximately 1 tablespoon of blood will be required.*
- *Comprehensive metabolic panel and CPK– approximately 1 tablespoon of blood will be required.*
- *Lipid panel – approximately 1 tablespoon of blood will be required.*
- *Urinalysis – approximately a cup of urine will be required.*
- *24-hour urine collection – approximately 4 cups of urine, collected throughout a day, will be required*

Physical examination including the cardiovascular, dermatological, respiratory and gastrointestinal and neurological organ systems and **vital signs, height and weight** will be performed at each scheduled and unscheduled visits.

EKG: EKG will be performed locally at Screening and Termination visits. Twelve-lead ECG should be performed following the participant being in a supine position for 5 minutes. The investigator will evaluate the ECG at time of performance (signed and dated) and the printout should be kept in the source documentation file. If the investigator detects potentially clinically significant findings, a cardiologist should be consulted for a definitive interpretation. All communications and diagnoses should be filed in the source documentation file.

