- CBC, CMP, CPK (8 ml of blood) and urinalysis with 24-hour urine collection
- Lipid panel (2 ml of blood)
- Sirolimus levels in blood (5 ml of blood)
- Adverse event reporting

In case the safety lab assessments are performed locally (e.g., at a local laboratory near the subjects' home), the PI or a licensed research member of the team will provide the patient with a prescription for the required tests. A research nurse, investigator or study manager will perform a phone call to assess adverse events within 7 days of the study visit.

To account for delays during the first month of treatment, Visit 7 (2-month) may be skipped to ensure that Visit 8 occurs 3 months (+/- 15 days) after the initiation of the study drug.

To maintain the blinding, the results of the sirolimus levels in blood will remain blinded to the investigators and study coordinators and delivered to the independent pharmacist in charge of determining if the sirolimus dosage should be increased or decreased.

End of study visit/early termination: the following tasks/procedures will be performed at the clinic during the termination visit (Study Visit 17):

- EKG
- MoCA
- Concomitant medications
- Physical examination
- Vitals signs
- CBC, CMP, CPK (8 ml of blood) and urinalysis with 24-hour urine collection
- Lipid panel (2 ml of blood)
- Sirolimus levels in blood (5 ml of blood)
- Retrieve study medication
- Recording of AE
- UMSARS scale
- Blood sample for exosomes (2 ml of blood)
- Retinal optical coherence tomography
- Brain MRI

We will accept a visit window of 15 days before or after the target date of this visit.

The reason for discontinuation of therapy will be documented in the source documents and captured on the CRF. In the event that the study drug is discontinued early, an early termination visit should be

completed as close to the last dose date as possible. Participants will be followed for the duration of 12 months.

If a participant is withdrawn because of an adverse event, the appropriate “Withdrawal Section” of the CRFs should be fully completed in addition to the Adverse Event module. The Independent Medical Monitor should be informed of all participants who are withdrawn for this reason. Participants will be followed for 12 months.

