4.4 END OF STUDY DEFINITION

A participant is considered to have completed the study if he or she has completed all phases of the study including the last visit or the last scheduled procedure shown in the Schedule of Activities (SoA), Section 1.3.

The end of the study occurs when the following circumstance have ALL occurred:

1. Completion of the last visit or procedure shown in the SoA in the trial globally.
2. Completion of data analysis
3. Completion of final study report

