7 STUDY INTERVENTION DISCONTINUATION AND PARTICIPANT DISCONTINUATION/WITHDRAWAL

7.1 DISCONTINUATION OF STUDY INTERVENTION

Discontinuation from study drug does not mean discontinuation from the study, and remaining study procedures should be completed as indicated by the study protocol. If a clinically significant finding is identified (including, but not limited to changes from baseline) after enrollment, the investigator or qualified designee will determine if any change in participant management is needed. Any new clinically relevant finding will be reported as an adverse event (AE).

The data to be collected at the time of study intervention discontinuation will include the following:

- EKG
- Concomitant medications
- Physical examination
- Vitals signs
- CBC, CMP, CPK, urinalysis
- 24-hour urine collection
- Lipid panel
- Sirolimus levels in blood
- Retrieve study medication
- Recording of AE
- UMSARS scale

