7.2 PARTICIPANT DISCONTINUATION/WITHDRAWAL FROM THE STUDY

Participants are free to withdraw from participation in the study at any time upon request. An investigator may discontinue or withdraw a participant from the study for the following reasons:

- Pregnancy
- Significant study intervention non-compliance
- If any clinical adverse event (AE), laboratory abnormality, or other medical condition or situation occurs such that continued participation in the study would not be in the best interest of the participant
- Disease progression which, in the opinion of the investigator, requires discontinuation of the study intervention
- If the participant meets an exclusion criterion (either newly developed or not previously recognized) that precludes further study participation
- Participant unable to receive study drug for 15 days or more.

The reason for participant discontinuation or withdrawal from the study will be recorded on the electronic Case Report Form (CRF). Subjects who sign the informed consent form and are randomized but do not receive the study intervention may be replaced. Subjects who sign the informed consent form, and are randomized and receive the study intervention, and subsequently withdraw, or are withdrawn or discontinued from the study, will not be replaced.

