9.4.4 SAFETY AND TOLERABILITY ANALYSES

Adverse events: The incidence and frequency of adverse events will be presented by System Organ Class and preferred terminology according to NCI and CTCAE reporting standard. Aes will also be presented by System Organ Class, High Level Term and preferred terminology. Data will be tabulated by treatment group, sex, age, maximal severity, maximal outcome, maximal action taken and maximal relationship to the tested drug. Serious adverse events and seriousness criteria will be listed and discussed on a case by case basis.

Laboratory tests: The incidence of laboratory tests outside the normal range and the incidence of measurements of potential clinical significance will be presented by treatment group. Shift analysis of these counts from baseline will also be provided. Descriptive statistics as well as their changes from baseline will also be presented by study group.

Vital Signs & Height/Weight: Incidence of measurements of potential clinical significance will be presented by study group. Shift analysis from baseline will be provided as well. Descriptive statistics of vital signs & height/weight, as well as, their changes from baseline, will be presented by study group.

EKG: The incidence of abnormal measurements will be presented by treatment group. Shift analysis from baseline will be provided as well. Descriptive statistics, as well as, their changes from baseline, will also be presented by study group.

Tolerability assessments: Tolerability analysis will be based on the number (%) of participants who failed to complete the study, the number (%) of participants who failed to complete the study due to adverse events. Time to withdrawal will be presented by Kaplan-Meier curves. Significance testing of time to withdrawal will be done using Cox's proportional hazards model.

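### The primary safety outcome and the tolerability analysis count leaving the study, not stopping study drug, so permanent stops of sirolimus for an adverse event can be undercounted

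*Combined protocol and SAP*

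**What the plan says.** Section 8.2 defines the outcome in one sentence: "The primary safety outcome is number of participants (%) who discontinue the study due to AE". Section 9.4.4 bases tolerability on the number who did not complete the study for any reason and on "the number (%) of participants who failed to complete the study due to adverse events. Time to withdrawal will be presented by Kaplan-Meier curves", with a Cox model for the significance test.

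Section 7.1 separates the two kinds of stopping: "Discontinuation from study drug does not mean discontinuation from the study, and remaining study procedures should be completed as indicated by the study protocol". Section 4.4 adds: "A participant is considered to have completed the study if he or she has completed all phases of the study including the last visit". Being on drug is not part of that definition.

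Section 7.2 begins: "An investigator may discontinue or withdraw a participant from the study for the following reasons". Its list includes an AE or laboratory abnormality that makes staying in the study contrary to the participant's interest, and an interruption of study drug of at least 15 days.

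Section 4.1 asks for an early termination visit when drug is stopped early. On participants withdrawn because of an AE it says: "The Independent Medical Monitor should be informed of all participants who are withdrawn for this reason. Participants will be followed for 12 months".

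**The concern.** Both headline tolerability measures are worded around study participation. Under 7.1 and 4.4, a participant who cannot tolerate sirolimus, stops it for good and keeps attending visits is a completer. That participant does not meet the 8.2 outcome. If withdrawal in 9.4.4 means leaving the study, the same person is censored in the Kaplan-Meier and Cox analyses. No listed outcome counts permanent discontinuation of study drug due to an AE.

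Two participants with the same toxicity can then be classified differently, one because the investigator used 7.2 and the other because the investigator followed 7.1. Better retention lowers the reported figure without any change in how well the drug is tolerated. A comparison of the arms would partly reflect that choice.

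**Working it through.** The documents state no expected rate, threshold or power for this outcome, so there is no figure of the plan's own to reproduce. The check has two parts.

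**The sections side by side.** Take a participant who permanently stops sirolimus for an AE and attends every later visit.

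- Under 7.1 the participant is still in the study.
- Under 4.4 the participant is a completer.
- Under 8.2 the participant is not counted.
- Under 9.4.4 the participant is not among "the number (%) of participants who failed to complete the study due to adverse events". Whether the stop is an event in the time-to-withdrawal analysis is open, because 9.4.4 does not define withdrawal.
- Under 7.2 the investigator may instead withdraw the participant, for the AE or for the drug gap. The participant is then counted in 8.2.
- Under 4.1 a participant can be recorded as withdrawn because of an AE and still be followed for 12 months. Such a person could be classified either way.

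The count is therefore not uniquely determined by the text.

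**Size, as an illustration.** Inputs: n = 42 planned on sirolimus (synopsis and 9.2); k = participants who permanently stop drug for an AE (assumed); w = probability that each is also withdrawn from the study (assumed, independent between participants).

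Expected reported percentage = k × w / 42. Chance that the report shows zero = (1 − w)^k.

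| k (k/42) | w = 0 | w = 0.25 | w = 0.5 | w = 0.75 | w = 1 |
|---|---|---|---|---|---|
| 4 (9.5%) | 0% | 2.4% | 4.8% | 7.1% | 9.5% |
| 8 (19.0%) | 0% | 4.8% | 9.5% | 14.3% | 19.0% |
| 12 (28.6%) | 0% | 7.1% | 14.3% | 21.4% | 28.6% |

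For k = 8 the chance of reporting zero is 1 at w = 0, 0.75^8 = 0.100 at w = 0.25, and 0.5^8 = 0.004 at w = 0.5. The outcome equals the number of AE-driven drug stops only at w = 1. It is certain to be zero only at w = 0.

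A reported 0/42 has a one-sided 95% upper bound of 1 − 0.05^(1/42) = 6.9%. That bound applies to leaving the study because of an AE. It says nothing about the rate of stopping drug.

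**The case against.** The strongest reply is that the protocol has several routes by which intolerance would show.

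- The 15-day item in 7.2 would fit most permanent stops, and 4.1 can be read as recording an AE-driven stop as a withdrawal even when follow-up continues. This stands as a limit on the size of the problem. It does not remove it, because 7.2 is permissive and 4.1 can be read both ways.
- AEs are recorded after drug is stopped (8.2), the reason for stopping therapy goes on the case report form (4.1), and 9.4.4 tabulates AEs by treatment group and by maximal action taken. This also stands in part. The action categories are not defined, and such a table is not a named count of participants by arm or a time-to-event analysis.
- The dose-limiting effects in 6.1.2 lead to dose reduction, with later re-challenge, so many toxicities would not lead to a permanent stop. This is correct, and it means that the word permanent needs a definition.
- Study discontinuation due to AE is a legitimate outcome. It is, once defined, but it answers a different question from whether participants could stay on drug.

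A reader might infer that real intolerance will be reported as zero, or that the phase III decision would be distorted. The documents support neither. Zero is assured only if every such participant is retained. The phase III decision rests on the UMSARS futility test (4.1, 9.4.2). The interim rules in 9.4.5 use UMSARS, and the trial-level safety rule in 10.1.2 uses the share of participants with frequent or severe adverse effects.

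**Conclusion.** The point holds at moderate severity. Sections 8.2 and 9.4.4 tie the safety and tolerability measures to leaving or not completing the study, while 7.1 and 4.4 allow a participant who has stopped drug to remain in it and complete it. Permanent AE-driven stops can be undercounted by anything from none of them to all of them, depending on the use of 7.2 and the reading of 4.1. The percentages above rest on assumed numbers of stops and assumed withdrawal probabilities, so they show the possible range and not a likely value. What is affected is a named primary safety outcome and a descriptive tolerability result. No go/no-go or stopping rule in the current text depends on either.

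**What to change.** - In 8.2, define the primary safety outcome as the number (%) of participants who permanently discontinue study drug due to an AE, by arm.
- In 9.4.4, make the Kaplan-Meier and Cox endpoint time to permanent study-drug discontinuation, once for all causes and once due to AE.
- Define permanent for analysis purposes in light of the re-challenge text in 6.1.2.
- Report study withdrawal due to AE as a separate line.
- Use discontinue and withdraw with one meaning each in 4.1, 7.1, 7.2, 8.2 and 9.4.4. How these sections are reconciled clinically is for the sponsor; no rule on stopping treatment is proposed here.
- State the denominator. Section 9.3 limits analyses to participants with at least 3 months of study drug and names no separate safety set, so early stops could otherwise be lost from the new count as well.

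The cost is mainly wording. The reason for stopping therapy is already captured on the case report form (4.1), and the date on which drug was stopped is listed among the source data (10.1.8.2). The reported figure may look less favourable than under the present definition.
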